# 4.2 Analysis Sets

The full analysis set (FAS) is defined as all subjects who have received the investigational product. All efficacy and safety analyses will be performed on the FAS.

### 4.3 Assessment Windows

For the purpose of listing and summarizing data, the time-in-study for each subject observation will be defined using study days. Such days will be measured relative to Day 0, the day in which the investigational product is received. Because protocol-specified visits (e.g., Day 30) will not necessarily occur on the same study day for all subjects, study visits will be defined through the use of windows. Study visits will have windows as per the following schema:

Spark Therapeutics AAV2-hCHM-101 Statistical Analysis Plan v3.0

Study Visit	Visit and Laboratory Testing Window
Study Day 0	Day of investigational product administration
Study Day 1	No window
Study Day 14	$14 \pm 2$ days
Study Day 30	$30 \pm 5$ days
Study Day 90	$90 \pm 30$ days
Study Day 180	$180 \pm 30 \text{ days}$
Study Day 365	$365 \pm 30$ days
Year 1.5	$547 \pm 30$ days
Year 2	730± 60 days

For evaluations after Year 2, the subject will go into the long-term follow-up phase. The subject returns to the clinic for follow-up at Years 2.5 and then annual follow-up, done in the clinic, for Years 3-5 for safety evaluations, standard ophthalmologic examinations, and retinal/visual function tests. The windows for the long-term follow-up visits are  $\pm$  60 days.

All data will be summarized by visit based on the visit in which the data was recorded in the database.

Baseline will be defined as the last pretreatment value during the screening period. If a repeat laboratory sample was drawn for a visit, only the repeat sample values will be listed or summarized. If there are repeated visual tests within the same visit, the average of all test results will be used for summary analysis. If there are more than one screening/baseline visit, the result from the later visit will be used for the analysis. Visual test results from all visits will be listed.

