#### 5.1.3 Laboratory Evaluations

Blood sampling will be performed for the following standard clinical laboratory evaluations (see Table 5.1.3.1); repeat analysis and/or additional sampling and testing will be performed when clinically indicated:

- Sequence analysis of the CHM gene by a CLIA-certified laboratory
- Hematology (CBC and differential)
- Chemistry panel to include liver and renal function tests
- Virology testing to include HIV screen

Urine testing will be performed by standard clinical laboratory analyses (see Table 5.1.3.1); repeat analysis and/or additional sampling and testing will be performed when clinically indicated:

• Urinalysis (UA) including pH, color, and microscopic exam

Analysis will be performed for the following research laboratory evaluations (see Table 5.1.3.2):

- AAV Viral Capsid Antibody
- PBMC for ELISpot
- Whole blood and serum for PCR analysis (vector shedding)

• Tears collected for vector shedding by PCR analysis

Category	Tests
CHM gene analysis	Sequence/mutation analysis by CLIA-certified laboratory
Hematology	CBC and differential
Chemistry panel	Standard panel per clinical laboratory (including liver and renal function tests)
Virology tests	Screening tests for HIV
Urinalysis	Standard urinalysis per clinical laboratory

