#### 8.2 Adverse Event Reporting

All events described by the subject will be reported as AEs, regardless of toxicity grade in.

Protocol-defined safety laboratory test results will be collected prospectively and analyzed separately as part of the study. Additional laboratory test results at other time points may be available to the Investigators as part of standard clinical practice. Throughout the active phase of the study, laboratory-related abnormalities should be recorded as AEs only if considered clinically significant, outside the range of expected values given the subject's baseline assessments and clinical course, and not known to be part of another AE diagnosis. As per regulatory guidelines, pre-existing conditions, including abnormal lab values manifest at baseline testing, will only be reported as adverse events if the condition worsens in severity and/or frequency.

The Investigators will follow an AE until the event is either resolved or assessed as stable.

The Investigators are responsible for notifying the Sponsor representative or designee and the IRB of all AEs and other unanticipated problems related to research. Unanticipated problems are other types of incidents, experiences, and outcomes that occur during the conduct of human subject research that are not considered adverse events. For example, some unanticipated problems involve social or economic harm instead of the physical or psychological harm associated with adverse events. In other cases, unanticipated problems place subjects or others at increased *risk* of harm, but no harm occurs.

The Sponsor or designee will notify the appropriate federal regulatory authorities (FDA, NIH OBA, DSMB). Events that do not require expedited reporting will be summarized at the time of continuing review / annual report.

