## 7.3 Clinical Laboratory Assessments

Laboratory assessments for hematology with differential, serum chemistries, urinalysis, AAV viral capsid antibody, PBMC for ELISpot, and vector shedding will be performed in accordance to the Schedule of Assessments in Appendix A.

Laboratory values will be presented in the data listings.

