### 8. **DSMB COHORT REVIEW**

In this trial, dose escalation will be contingent upon DSMB approval following review of the safety and efficacy data through at least 30 days for all subjects in the prior cohort. The data for DSMB analysis will be presented as described above. Following each DSMB meeting, the DSMB will

provide the Sponsor with written recommendations related to continuing, changing, or terminating the trial.

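### SAP 4.3 lists only the repeat when a laboratory sample is repeated for a visit, so a valid abnormal original that clears and is not an AE appears in no planned output

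*SAP*

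**What the plan says.** SAP 4.3 (Assessment Windows) sets the rule: "If a repeat laboratory sample was drawn for a visit, only the repeat sample values will be listed or summarized". It does not say why a sample might be repeated and does not limit the rule to unusable specimens. The same section says that "study visits will be defined through the use of windows", and then that "All data will be summarized by visit based on the visit in which the data was recorded in the database".

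SAP 7.3 gives the whole laboratory output in one sentence: "Laboratory values will be presented in the data listings". It plans no summary, shift or abnormality table. The SAP revision table says this sentence was worded to agree with Section 4.3. SAP 8 carries the presentation over to the dose-escalation review: "The data for DSMB analysis will be presented as described above".

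Protocol 5.1.3 says that "repeat analysis and/or additional sampling and testing will be performed when clinically indicated". Protocol 8.2 says: "Protocol-defined safety laboratory test results will be collected prospectively and analyzed separately as part of the study". It also limits which laboratory findings become AEs: "Throughout the active phase of the study, laboratory-related abnormalities should be recorded as AEs only if considered clinically significant". They must in addition lie outside what is expected for the subject and not belong to another AE diagnosis.

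**The concern.** Using one value per visit in a summary is ordinary practice. Taking the other value out of the listing is not, and here the listing is the only place where a laboratory abnormality that is not an AE would be seen. Protocol 8.2 relies on laboratory results being examined separately from AEs, and under this SAP the listing is all of that examination.

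Repeats may be drawn for clinical reasons, and an abnormal first value is a plausible trigger (an inference; the documents do not say so). The rule may therefore remove the values a safety reader would look for. A reader of the report, or the DSMB in its laboratory data, could not see that a valid abnormal value occurred and then cleared. With 15 subjects, no hypothesis tests and safety as the primary objective, single values are the evidence.

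SAP 4.3 treats visual tests differently. Repeats within a visit are averaged for summary, and results from all visits are listed.

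**Working it through.** The plan gives no figure to reproduce. The check follows one value through the planned outputs, then counts the scheduled panels the rule covers.

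**Path of the value.** Take an original that is valid and abnormal, with a repeat drawn for the same visit, a repeat that no longer shows the abnormality, and no AE recorded.

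| Planned output | Does the original appear? | Reason |
|---|---|---|
| Laboratory listing (SAP 7.3) | No | SAP 4.3 lists the repeat only |
| Laboratory summary | No | None planned; SAP 4.3 would exclude it anyway |
| AE tables and listing (SAP 7.2.5) | No | Not recorded as an AE (Protocol 8.2) |
| DSMB data (SAP 8) | No | Same presentation |

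SAP 4 also says in general terms that subject data are listed. That does not restore the original, because the specific sentence in 4.3 governs.

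**How far apart the two draws can be.** The largest gap between two draws inside one window is the full window width:

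- Day 14 (±2): 2 × 2 = 4 days
- Day 30 (±5): 2 × 5 = 10 days
- Days 90 and 365 (±30): 2 × 30 = 60 days
- Year 2 and Years 3–5 (±60): 2 × 60 = 120 days

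These are maxima, and both draws must be recorded under the same visit. If the recheck is recorded under another visit, it does not replace the original.

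**Scheduled post-dose panels** (Table of Clinical Assessments; Protocol 4.2.2 and 4.5), assuming all 15 subjects attend every visit:

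| Panel | Active-phase visits | Count | Years 3–5 |
|---|---|---|---|
| Hematology | Days 1, 3, 14, 30, 90, 365; Year 2 | 7 | 3 |
| Chemistry | Same | 7 | 3 |
| Urinalysis | Days 1, 3, 14, 365; Year 2 | 5 | 3 |

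- Active phase: (7 + 7 + 5) × 15 = 285
- Years 3–5: (3 + 3 + 3) × 15 = 135
- Total: 285 + 135 = 420
- Cohort 1 through Day 30: (4 + 4 + 3) × 5 = 55
- Visits with a 60- or 120-day window: Day 90 (2) + Day 365 (3) + Year 2 (3) + Years 3–5 (9) = 17; 17 × 15 = 255; 255/420 = 61%
- The same, active phase only: (2 + 3 + 3) × 15 = 120; 120/285 = 42%

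Screening and Day 0 draws are not counted. Nor are capsid antibody, ELISpot and vector shedding, although SAP 7.3 puts these three assays under the same listings.

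**The case against.** The strongest reply is that a repeat drawn for a visit may mean only a redraw of an unusable specimen, in which case dropping the original is harmless. The documents do not settle this. The sentence in 4.3 has no such limit, and Protocol 5.1.3 allows repeats on clinical grounds. The mix of technical redraws and clinical rechecks is unknown.

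Other points stand as limits:

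- **Windows.** Assignment follows the visit recorded in the database, so window width alone does not decide whether an original is replaced. The gaps show what the rule permits; they do not predict what sites will do. The 61% describes scheduled windows, not hidden values.
- **Counts.** The 420 is a count of scheduled panels. The rule acts only on those that are repeated.
- **After Year 2.** The Protocol 8.2 restriction on laboratory AEs covers the active phase only. At Years 3–5 the AE route depends on the document: Protocol 4.5 records all AEs, while SAP 7.2 records only related serious events and four disease categories. That conflict is separate, so the case is clearest for the 285 active-phase panels.
- **DSMB.** The board reviews all AEs (Protocol 8.8), and the stopping rules in Protocol 7.4 rest on graded toxicity possibly or probably related to the vector. No escalation or stopping decision has been identified that would change.
- **Summary rule.** Removing the sentence might seem to leave open which value enters a summary. SAP 7.3 plans no laboratory summary, and SAP 4.3 already defines baseline as the last pretreatment value in screening. A rule would be needed only if a summary were added.

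**Conclusion.** The concern holds, at minor severity. An original laboratory value appears in no planned output when four conditions are met together: it was valid and abnormal, a repeat was recorded for the same visit, the repeat no longer shows the abnormality, and no AE was recorded. Whether the original is shown also depends on the visit under which the site records the recheck.

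The number of values affected is unknown, and no probability of a hidden signal can be derived. The panel counts bound only where the rule could act on hematology, chemistry and urinalysis, and they assume full attendance by 15 subjects. Abnormalities confirmed by the repeat remain listed, and clinically significant active-phase findings still reach readers and the DSMB as AEs. What is lost is display in the planned outputs; nothing in the SAP says that source data are discarded.

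**What to change.** Replace the repeat-sample sentence in SAP 4.3 with:

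> All laboratory values, original and repeat, will be listed with collection date, a repeat flag, and a flag for any specimen documented as invalid; no value is removed from the listing.

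Unusable specimens remain identifiable, so the legitimate purpose of the present rule is kept. SAP 7.3 and SAP 8 need no change, because the listings and the DSMB data follow from 4.3. The cost is one sentence and slightly longer listings. No new visits or data are needed, provided the original values are in the database; the sponsor should confirm this.

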# 4.4 Handling of Dropouts or Missing Data

Missing data will remain missing. No imputation of missing data will be performed.

### 4.5 Multiple Comparisons

No multiple comparisons are planned for this study.

#### 4.6 Data Derivations and Transformations

Not applicable.

### 5. STUDY SUBJECTS

### 5.1 Disposition of Subjects

A table of counts of all enrolled subjects will be provided. Reasons for not completing study medication as planned and reasons for premature withdrawal will be tabulated for each dose cohort.

### 5.2 **Protocol Deviations**

A listing of all protocol deviations will be provided.

### 5.3 Demographic and Baseline Characteristics

All demographic characteristics including age, gender, race, ethnicity, height, and weight will be summarized using the FAS for the cohorts. Baseline characteristics including abnormalities of past ocular history for both injected and control eyes, and genetic analysis of *CHM* gene will be summarized and listed using the FAS. HIV test will be provided in a data listing.

### 5.4 Medical History

All medical conditions and surgical procedures will be classified by system organ class (SOC) and preferred term (PT) using the Medical Dictionary for Regulatory Activities (MedDRA). The number and percent of subjects with each medical condition and surgical procedure will be presented for each SOC and PT for the FAS subjects.

#### 5.5 **Prior and Concomitant Medications**

Concomitant medications will be coded using World Health Organization (WHO) drug classifications. The number and percent of FAS subjects using concomitant medications will be tabulated by default Anatomical, Therapeutic, and Chemical (ATC) class and by preferred name.

### 6. EFFICACY ANALYSIS

Safety is the primary objective of this study. All efficacy analyses are strictly exploratory.

#### 6.1 Exploratory Efficacy Analyses

Each of the exploratory efficacy evaluations, which are described below, will be listed by injected and control eyes for each subject at each visit, grouped by cohort. The time points of each parameter assessments are presented in the Appendix A.

#### 6.1.1 Visual Acuity

Visual acuity measures will document any change in central vision, the ability to resolve standard optotype images presented as optotypes/letters corresponding to different visual angles, *i.e.*, image size. This testing will use ETDRS charts. The level of central visual resolution is converted to a visual angle score (LogMAR) for comparison purposes. The reliability of the results, calculated visual acuity, LogMAR acuity score, and the method used for no optotype recognition will be listed for each tested distance.

#### 6.1.2 Visual Field Tests

Visual field parameters will evaluate alterations in function of different regions of the retina; kinetic fields will be measured with Goldmann (III4e isopter), and Humphrey static fields with computerized testing, including foveal and macular thresholds, and a central field. In addition, Octopus kinetic perimetry will be done to subjects whose central visual field is >20° in at least 1 of the 24 meridians at Screening/Baseline visit using Goldmann perimetry III4e isopter.

Results from Goldmann visual field test: the reliability of the results, the total number of degrees

for all 24 meridians using the III4e test stimulus, and the number of the 24 meridians  $< 30^{\circ}$  will be listed.

A list of Humphrey visual field test results will be presented for the variables including the reliability of the results, mean deviation, mean threshold, and foveal sensitivity from Humphrey 30-2 test and10-2 test.

A list of Octopus kinetic visual field test results will be presented for the variables including III4e visual field, III4e scotomas, V4e visual field, V4e scotomas, reaction time, duration, and reliability.

# 6.1.3 Reading Speed

The reading speed test will require subjects to read designated word slides with different levels of contrast between letters and background aloud and subsequently, the reading accuracy and speed will be reported. The time (seconds), number of words missed, number of extra words read, number of times re-read words, and the reason for not passing the test, if applicable, will be listed for each slide. Additionally, the reading speed (wpm), maximum reading speed (wpm), and critical print size will also be listed if the Minnesota Low-Vision Reading (MNREAD) test was performed.

### 6.1.4 Contrast Sensitivity

Contrast sensitivity will measure the subject's ability to discern targets presented at varying levels of contrast. The variables of measurements include the log contrast sensitivity and the pupil diameter.

### 6.1.5 Color Vision Test

Color vision testing will be conducted and the results will be listed at each visit.

### 6.1.6 Microperimetry

Microperimetry will be conducted in the dark-adapted state to evaluate maximal retinal sensitivity. Microperimetry measurements of the injected eyes will also be compared to the control (uninjected) eyes. The mean macula threshold and foveal sensitivity will be presented in a data listing.

### 6.1.7 Full-field Light Sensitivity Threshold Testing

Full-field light sensitivity threshold (FST) testing measures the light sensitivity of the entire visual field by recording the luminance at which a subject reports seeing the dimmest flash. The light sensitivity of each eye is measured separately by removing patches from one eye (and then the other). A sound is generated at the time of the light flash and the subject presses one button when they see a flash or a second button if they do not see a flash. Flashes of varying luminance (in a range spanning ~100 dB) are presented in a randomized order, except that the series starts with dim flashes. From this data, an algorithm calculates the minimum luminance (for each eye) at which the subject perceives light.

The results of light sensitivity measurements from each test, and the average of all reliable tests results will be listed for each of the light sources (White, Red, and Blue lights).

## 6.1.8 Fundus Photography

Fundoscopy will be performed with indirect ophthalmoscopic exam and fundus biomicroscopy. Photographs will be taken with a fundus camera following standard clinical methods. The variables including the interpretability of the photograph, the reason not interpretable, the area of retina without confluent atrophy, and the estimated area of intact RPE in disc areas will be listed.

## 6.1.9 Optical Coherence Tomography (OCT)

OCT captures micrometer-resolution, three-dimensional images from within optical scattering media (*e.g.*, retinal tissue). The Heidelberg Spectralis OCT machine will be used. Optical coherence tomography is an interferometric technique, typically employing near-infrared light. The use of relatively long wavelength light allows it to penetrate into the scattering medium, providing important images, including the thickness of the retina. The listed variables will include the reliability of the fast macular thickness map scan, the reason for unreliable scan, foveal thickness, macular volume, and the presence of subretinal and intraretinal fluid.

### 6.1.10 Quality of Life (QOL) Questionnaire

The Investigators will use a QOL questionnaire relevant to the subject population and a final score will be calculated. The final score (average of all numeric responses) will be listed at each visit.

### 6.2 Pharmacokinetic Analysis

No pharmacokinetic analysis is planned for this study.

### 7. SAFETY ANALYSIS

Safety assessments will include adverse events, clinical chemistry, hematology (complete blood count and differential), urinalysis, AAV viral capsid antibody, PBMC for ELISpot, vector shedding assessment, ophthalmic examination, vital signs, and physical examination.

All safety summaries (or analyses if applicable) will be conducted using the FAS. No formal hypothesis testing will be performed to compare differences between the cohorts.

#### 7.1 Extent of Exposure

The actual dose received, estimated sub-retinal volume injected, estimated air fluid exchange, total number of injection-retinotomy sites, and the total number of successful injection-retinotomy sites will be summarized for each dose cohort. A listing of the data will also be presented.

#### 7.2 Adverse Events

All adverse events (AEs) including serious adverse events (SAEs) will be recorded through the Year 2 visit following investigational product administration. Following the scheduled Year 2 visit, adverse event recording will occur for any related serious adverse events, or for the development of any oncologic, hematologic, neurologic or autoimmune events.

An AE is any untoward, undesired, or unplanned clinical event in the form of signs, symptoms, disease, or laboratory or physiological observations occurring in a subject participating in a clinical study with the Sponsor's investigational product, regardless of causal relationship. AEs will

include any conditions that: 1) were not present prior to investigational product administration, but appeared following investigational product administration; or 2) were present prior to investigational product administration, but worsened in severity and/or frequency following investigational product administration.

